5.6.2.2.2 Sensitivity analysis/analyses

No sensitivity analyses have been defined.

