	Known primary immunodeficiency disorder.								
Investigational medicinal product	Name/active substance: tralokinumab (human recombinant IL-13 monoclonal antibody of the immunoglobulin G4 subclass that specifically binds to human IL-13 and blocks interaction with the IL-13 receptors).								
	 Dosage form: solution (in accessorised pre-filled syringe, 1.0 mL fill volume). 								
	• Concentration: 150 mg/mL.								
	 Dose for adult subjects from all parent trials, except the parent trial LP0162-1334: 600 mg initial loading dose, then 300 mg every second week. 								
	• Dose for subjects from the parent trial LP0162-1334*: 300 mg every second week.								
	*All subjects from the parent trial LP0162-1334, independent of the subject's age when included in ECZTEND.								
	Method of administration: subcutaneous injection.								
Duration of treatment	The duration of the treatment period for each subject will depend on when the subject enters the trial after completing the parent trial, and by which treatment stop date they have consented to (end of May 2021, end of May 2022, or a country-specific end of treatment day):								
	• For subjects who did NOT re-consent to participate in the trial after May 2021, trial treatment was stopped by end of May 2021. Treatment duration was maximum 140 weeks.								
	• For subjects from the parent trial LP0162-1334 who consented to participate in the trial after May 2021, trial treatment will be stopped by end of May 2022. Treatment duration will be maximum 114 weeks.								
	• For subjects from the parent trials LP0162-1325, -1326, -1339, -1341, -1342, -1343, -1346, and TRA-WEI-0015-I who consent to participate in the trial after May 2021, trial treatment will be stopped at a country-specific treatment completion date. Treatment duration will be maximum 268 weeks.								
Number of subjects	It is assumed that approximately 1,600 subjects will be assigned to treatment.								
Number and distribution of trial sites	Approximately 330 sites in Canada, Europe, Japan, and the US.								
Statistical methods	Primary endpoint AEs will be summarised for all treated subjects (full analysis set) and will be presented by Medical Dictionary for Regulatory Activities (MedDRA) preferred term and primary system organ class (SOC) as percentage of subjects with AEs, number of AEs, and rate of AEs (number of AEs per 100 patient-years of exposure).								

Page 22 of 187

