14.3.6 Other endpoints

Changes from baseline in EASI score and SCORAD will be presented as number of observations (N), mean, standard deviation (SD), median, minimum, and maximum at each assessment visit. The baseline scores used will be those from the parent trial.

The changes from baseline in EASI score and SCORAD will be presented for the FAS as well as for the observed cases.

3 endpoints addressing treatment effect during the treatment period will be included:

- Proportion of time with EASI75 after first occurrence of EASI75 during treatment.
- Proportion of time with EASI50 after first occurrence of EASI50 during treatment.
- Proportion of time with IGA 0/1 after first occurrence of IGA 0/1 during treatment.

The proportion of time with EASI75 for an individual subject will be calculated as the time with EASI75 (that is, the sum of time intervals with EASI75) divided by the observation period after first occurrence of EASI75. The time intervals in which EASI75 is observed at the start of the interval will be accumulated and normalised with the total treatment time from first EASI assessment with EASI75 until end of treatment.

The proportion of time with EASI50 and with IGA = 0/1 after first occurrence during treatment will be determined using the same principle as for the proportion of time with EASI75.

These 'proportion of time' endpoints will each be presented as number of observations (N), mean, SD, median, minimum, and maximum. The group mean comprising the summed nominators (of time) divided by the summed denominators will further be presented.

As the frequency of site visits is reduced after May 2021, a sensitivity analysis excluding data captured after May 2021 will be performed for the 'proportion of time' endpoints. For exploratory purposes, the proportion of subjects achieving EASI75 will be plotted versus the proportion of time with EASI75 (ranging from 0–100% of the observation period after first occurrence of EASI75). Similar plots for EASI50 and IGA 0/1 will be shown in the same graph.

The results for the endpoints described in this section will be presented for the total cohort of subjects and by tralokinumab-naïve/re-treated/continuously treated subjects. For the re-treated

and continuously treated subjects, the results will further be divided by responder/non-responder in the parent trial (clinical response as defined in Section 14.3.5).

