14.2 Trial analysis sets	Added text: Data from the investigator-initiated parent trial TRA-WEI-0015-I will not be transferred to LEO Pharma. Thus, endpoints defined as change from baseline (in parent trial) will not be calculated for subjects from this trial,	To clarify to what extent data from the parent trial TRA-WEI-0015-I will be included in endpoints and summarised data presentations.

Section number and name	Description of change	Brief rationale
	and data from this trial will not be included in tables summarising endpoints defined as change from baseline or where data are presented by responder/non-responder. Subjects from this parent trial will be contributing to the primary endpoint and included in summary tables where possible.	
14.3.4 Primary endpoint	The primary endpoint in this trial is number of adverse events during the treatment period from baseline up to Week 142 268, and the analysis of this is covered in Section 14.3.8.	To reflect the extended treatment period.
14.3.6 Other endpoints	An analysis has been added: As the frequency of site visits is reduced after May 2021, a sensitivity analysis excluding data captured after May 2021 will be performed for the 'proportion of time' endpoints.	Sensitivity analysis added as the less frequent assessment of efficacy after May 2021 could influence the estimation and precision of the 'proportion of time' endpoints.
14.3.7 Patient-reported outcomes	Added text: In the special case where a subject has an assessment at both Week 80 and Week 88, the Week 80 assessment (corresponding to approximately 1½ years) will be used for the Week 80-88 endpoint evaluation. Likewise, the Week 128 assessment (~ 2½ years) will be prioritised for the Week 128-136 endpoint evaluation. Changes from baseline will not be presented for subjects from the parent trial TRA-WEI-0015-I, since data from this investigator-initiated trial will not be transferred to LEO Pharma (see Section 14.2).	To clarify the handling of the Week 80-88 and Week 128-136 endpoints. To clarify that data from the parent trial TRA-WEI-0015-I will not be included in change from baseline endpoints for patient-reported outcomes.

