5.6.2.2 Proportion of response over time endpoints

5.6.2.2.1 Primary analysis

The proportion of response over time will be estimated by the AUC over daily responses estimated through linear interpolation between observed assessments made at scheduled visits. The analysis will calculate the mean proportion (assumed continuous) and 95% Wald CI appended, with the standard deviation, median, 1st and 3rd quartiles, and minimum and maximum values appended as well.

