5.6.2.2.3 Supplemental analyses

A supplementary analysis will be appended for the primary analysis, where each estimated percentage of days in response will be used to analyse the endpoint rephrased in to "subjects with $\geq x\%$ of days in response" where x is defined as the whole numbers 0, 1, 2, ...,100. The subsequent proportion of subjects with $\geq x\%$ of days in response will be estimated with 95% Wilson CIs.

The second supplementary analysis, will be re-made for the primary and the above supplemental analysis over the following periods: Week 0-<16, Week 16-<104, Week 104-<200, and Week 200-264, in addition to the overall treatment period.

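### The SAP defines no sensitivity analysis for the three proportion-of-time endpoints, although Protocol 14.3.6 commits to one excluding data after May 2021, and its list of changes does not explain the difference

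*SAP*

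**What the plan says.** Protocol 14.3.6 defines three endpoints: the proportion of time with EASI75, with EASI50 and with IGA 0/1, each counted from its first occurrence on treatment. It gives the visit change after May 2021 as the reason why "a sensitivity analysis excluding data captured after May 2021 will be performed" for them. Appendix 8 (Amendment 7, entry for 14.3.6) records the sponsor's reasoning: "the less frequent assessment of efficacy after May 2021 could influence the estimation and precision" of these endpoints.

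The same protocol section fixes the counting rule: "The time intervals in which EASI75 is observed at the start of the interval will be accumulated". It adds a pooled summary: "The group mean comprising the summed nominators (of time) divided by the summed denominators will further be presented".

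SAP 5.6.2.2 covers the same endpoints. Its primary analysis (5.6.2.2.1) uses daily responses obtained by "linear interpolation between observed assessments made at scheduled visits". On sensitivity analyses, 5.6.2.2.2 says "No sensitivity analyses have been defined". The supplemental analyses (5.6.2.2.3) are curves of the share of subjects with at least x% of days in response, and repeats "over the following periods: Week 0-<16, Week 16-<104, Week 104-<200, and Week 200-264".

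SAP Section 1 says that changes to protocol-planned analyses are described in Section 6. Panel 5 there has two rows, both for Protocol 14.3.5.

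**The concern.** After May 2021 efficacy is scored only at site visits, which from Week 24 are 16 weeks apart instead of 8 (Panel 5 against Panels 3 and 4). With wider spacing, a relapse that comes and goes between two good visits is counted as response. A remission missed between two poor visits works the other way, so the mean should move little. The imbalance should appear at the top of the days-in-response curves, where sustained control is read. The protocol planned a check for this, and a programmer working from the SAP alone would not produce it.

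The counting rule matters for the same reason. Suppose response is lost halfway through a 16-week gap. Start-of-interval counting credits 16 weeks; interpolation credits 16 / 2 = 8. If response is gained halfway, the credits are 0 and 8. A reader of the report would not learn from Panel 5 that the rule had changed.

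**Working it through.** **1. Side by side.**

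| Item | Protocol 14.3.6 | SAP | Listed in Panel 5? |
|---|---|---|---|
| Analysis without data after May 2021 | Will be done, three endpoints | 5.6.2.2.2: none defined | No |
| Counting rule | Status at start of interval | 5.6.2.2.1: daily linear interpolation | No |

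The May 2021 split is not dropped everywhere. For adverse events, SAP 5.8.1 keeps the table excluding later data and adds one restricted to later data.

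**2. Can the study-week periods stand in for the calendar cut?** Place end of May 2021 on the study-week scale.
- On the 8-weekly schedule the end-of-treatment visit falls at Week 140 at the latest (Protocol Panel 4 and its footnote 2). The synopsis line "Treatment duration was maximum 140 weeks" agrees, but it covers only subjects who did not re-consent. Since 104 < 140 < 200, the longest-treated subjects change schedule inside the Week 104-<200 period.
- Subjects from LP0162-1334 have at most 114 weeks by end of May 2022 (synopsis), so about 114 - 52 = 62 weeks at end of May 2021. That lies inside the Week 16-<104 period.
- Only Week 200-264 lies wholly on the later schedule.

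The two long middle periods therefore mix 8- and 16-weekly data, and no period isolates data from before the change.

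**3. How large could the effect be?** The documents give no response level or fluctuation rate, so all inputs here are assumed.
- Model: latent severity = subject effect + weekly AR(1) fluctuation with autocorrelation exp(-1/tau). The response threshold is set to the assumed mean response. The score is interpolated linearly, and time runs from the first visit in response to the last visit.
- Inputs: mean response 60, 75 or 85%; tau 4, 8 or 16 weeks; between-subject variance share 0.3, 0.5 or 0.7. All 27 combinations, 40,000 subjects each.
- 8-weekly visits: Weeks 0, 2, 4, 8, 12, 16, 24, then every 8 weeks to 96.
- Mixed visits: the same to Week 48, then 56, 72, 88 and 96 (96 taken as the end-of-treatment visit).

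Differences in percentage points (pp), range over the 27 settings:

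| Comparison | Mean | >=90% of days | 100% of days |
|---|---|---|---|
| Mixed minus 8-weekly, to Week 96 | +0.1 to +0.6 | +0.9 to +2.4 | +1.5 to +3.3 |
| Interpolation minus start-of-interval counting, mixed visits | -1.6 to +2.4 | -0.1 to +7.3 | -3.0 to -1.3 |

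A repeat with 8,000 subjects per setting put the top of the first mean range at +0.9, so under about 1 pp is the safe statement. With the switch at Week 72 (9 of the 27 settings), the mean moves 0.0 to +0.3 and the 100% share +0.7 to +1.6.

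**4. What a plain calendar cut would show.** In the same model, data cut at Week 56 lie above mixed data to Week 96 by +0.1 to +3.6 pp in the mean and +4.3 to +11.2 pp in the 100% share. Much of that gap comes from shorter follow-up: fewer weeks leave less chance of a recorded lapse.

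**The case against.** The best defence is that SAP Section 1 says the analysis follows protocol version 14.0 and that the SAP supplements the protocol. On that reading, 5.6.2.2.2 adds nothing beyond the protocol and the planned analysis still stands. Protocol 14.3.11 also lets a change be justified as late as the clinical trial report. This has some force: a reader might infer that the analysis has been deliberately removed, and the documents do not show that. They show an unreconciled conflict. The defence does not dissolve it, because an express statement that none is defined differs from silence, and the SAP names its own Section 6 as the place for changes.

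Second, the stakes are small. These are other endpoints, SAP Section 2 specifies no testing, and the days-in-response curves are supplementary. This stands and sets the severity.

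Third, the protocol's own analysis would not isolate visit spacing, since the cut also shortens follow-up. This also stands. It is a reason to interpret the result with care, and could be a reason for dropping the analysis if the SAP gave it.

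A reader might also infer that the pooled ratio of summed times has been dropped. The SAP merely does not mention it, and silence does not establish removal.

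**Conclusion.** The conflict is in current text and holds. The SAP defines no sensitivity analysis where the protocol commits to one, its week-based periods do not substitute for it, and neither this nor the change of counting rule is in Panel 5. The severity is minor: only descriptive other endpoints are touched, and the primary and secondary endpoints are unaffected.

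The sizes are illustrative. They rest on assumed response levels and fluctuation rates, on response being stable from Week 0 (no onset phase for naive or re-treated subjects), and on one switch week. A tempting larger figure comes from running the later schedule throughout, where the 100% share rises by +4.1 to +9.5 pp. That describes only subjects who entered after May 2021. The pooled cohort also contains subjects who never moved to the later schedule and subjects with country end dates from August 2021 to May 2024. No calculation here averages over that mix, so the pooled effect is unknown. Within the model, the unlisted change of counting rule can move results more than the visit spacing does.

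**What to change.** - In SAP 5.6.2.2.2, restore the analysis excluding data captured after May 2021 for all three endpoints. If leaving it out is deliberate, add a Panel 5 row citing Protocol 14.3.6 with the reason.
- Add a Panel 5 row for the move from start-of-interval counting to linear interpolation, with the reason.
- State next to the restored analysis that the cut also shortens follow-up, so a difference from the main result is not due to visit spacing alone. Optionally, add a comparison over the same window, for example by thinning visits before June 2021 to the later schedule while keeping Weeks 0, 2, 4, 8, 16 and 24. Neither document plans this.
- Confirm whether the pooled ratio of summed times will be presented.

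The cost is a few lines in SAP 5.6.2.2 and Panel 5 and a rerun of existing programs on date-filtered data (and on thinned data, if that option is taken). No new data are needed.

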5.6.2.2.3 Supplemental analyses

A supplementary analysis will be appended for the primary analysis, where each estimated percentage of days in response will be used to analyse the endpoint rephrased in to "subjects with $\geq x\%$ of days in response" where x is defined as the whole numbers 0, 1, 2, ...,100. The subsequent proportion of subjects with $\geq x\%$ of days in response will be estimated with 95% Wilson CIs.

The second supplementary analysis, will be re-made for the primary and the above supplemental analysis over the following periods: Week 0-<16, Week 16-<104, Week 104-<200, and Week 200-264, in addition to the overall treatment period.

5.7 Pharmacokinetics analysis

The pharmacokinetics analysis is tabulated as described in the CTP Section 14.3.9.

5.8 Safety analysis

Safety endpoints will be analysed using the SAF.

5.8.1 Adverse events

AEs will be coded during the course of the trial according to MedDRA version 20.0 but analysed in MedDRA version 27.0.

Only TEAEs will be summarized in this trial. AEs were considered treatment emergent if they started after first dose of IMP or started before first dose of IMP and worsened in severity after first dose of IMP. All AEs recorded during the trial will be listed.

For the treatment and SFU periods, presentations of AEs by SOC and PT will include summaries of the following categories of AEs:

- All AEs.
- Frequent AEs (\geq 5% of subjects reporting the AE in the total population).
- Frequent AEs (occurring with an incidence rate ≥ 2.5 in the total population).
- SAEs.
- AEs leading to withdrawal from the trial.
- Probably or possibly related AEs.
- Severity of AEs (mild, moderate, and severe AEs presented separately).

Summaries will include the percentage and number of subjects with an AE, number of AEs, patient-years of exposure up until the first event, incidence rate of AEs (rate of new events/occurrences, calculated as the number of subjects with an AE per 100 patient-years of exposure at risk defined as patient-years up until the first event or end of exposure [whichever came first]), and occurrence rate of AEs (rate of events/occurrences calculated as the number of AEs per 100 patient-years of exposure up until end of exposure).

Overviews of AEs will be appended for the above-mentioned categories of AEs and will include the following information: SAEs, severity (mild, moderate, or severe), relationship to IMP (probably, possibly, and not related), AEs probably or possibly related to IMP, AEs leading to withdrawal from trial and/or permanent discontinuation of IMP, outcome, and action taken with IMP.

For the SFU period, all AEs and SAEs will be presented by an overview summary and by SOC and PT using the safety follow-up analysis set.

The above summaries will also be made separately for subjects who transferred from the parent trial LP0162-1334. Secondly, as the frequency of site visits is reduced after May 2021, 2 additional overall AE summary tables will be presented, one will exclude events and exposure time after May 2021 and the second will only include events and exposure time after May 2021. Thirdly, the data will be presented by tralokinumab naïve, re-treated, and continuously treated, and by washed-out subjects using the above defined summaries.

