EuroQoL 5-Dimension Health Questionnaire 5-Level ⁸			X			X	X		X	X	11.3.2.3	
Worst Weekly Pruritus numeric rating scale ⁹ Eczema-related Sleep numeric rating scale ⁹ Patient use of topical treatment ¹⁰	X	X	X	X	X	X	X		X	Х	11.3.2.4	

- 1) Subjects who withdraw from the trial will be followed up as described in Section 10. The final safety follow-up visit will be 16 weeks after the last dose (i.e. 14 weeks after the EOT visit).
- 2) The number of weeks until the EOT visit (2 weeks after the last dose of tralokinumab, maximum 140 weeks) and SFU visit (maximum 154 weeks) for each subject will depend on the time of their trial entry and treatment duration.
- 3) Assessments and procedures to be performed at an unscheduled visit are at the discretion of the investigator. If the unscheduled visit involves administration of rescue treatment, the investigator should make every attempt to conduct efficacy and safety assessments (at least disease severity scores [IGA and EASI], concomitant medications/procedures, and AEs) immediately before administering any rescue treatment (see Section 9.5).
- 4) If the date of a trial visit does not conform to the clinical trial protocol, subsequent visits should be planned to maintain the visit schedule relative to baseline.

Trial ID: LP0162-1337

5) At trial visits, tralokinumab will be injected at the trial site, preferably by the subject or their caregiver, alternatively by site staff. At each trial visit, subjects will be provided with tralokinumab to be administered at home until the next trial visit. In case of intercurrent illness that may compromise the safety of the subject, or fever within 72 hours prior to administration, tralokinumab administration should be rescheduled. If an anaphylactic reaction occurs, blood samples should be drawn for the analysis of serum tryptase (see details in Section 9.2).

- 6) Urine samples will be tested at the trial site (dipstick). In case of abnormal dipstick results, a urine sample will be sent to the central laboratory for microscopic examination (leucocytes, erythrocytes, and casts) (Section 11.4.5).
- 7) Adult subjects from all parent trials, except the LP0162-1334 trial, will perform the DLQI. Subjects from the parent trial LP0162-1334 will perform the CDLQI, independent of the age of the subject during participation in ECZTEND.
- 8) Subjects from the parent trial LP0162-1334 will not perform the EuroQoL 5-Dimension Health Questionnaire 5-Level.

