- 9) Subjects from the parent trial LP0162-1334 will perform an adolescent's pruritis NRS with a recall period of past 7 days, and an eczema-related sleep NRS with a recall period over the past 7 nights, independent of the age of the subject during participation in ECZTEND.
- 10) Based on subject recall during the last week prior to each site visit (from 6 days prior to each visit and including the day of the visit).

Abbreviations: CDLQI = Children's Dermatology Life Quality Index; DLQI = Dermatology Life Quality Index; EOT = end of treatment, 2 weeks after the last dose of tralokinumab; NRS = numeric rating scale; SFU = safety follow-up.

Page 34 of 187

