Weeks since first treatment in LP0162- 1337	-2	0	2	4	8	16	24	32 64 96 128 160 192 224 256	40 72 104 136 168 200 232 264	48 80 112 144 176 208 240	56 88 120 152 184 216 248	Variable ² (max 268)	SFU visit Variable ²	Un- scheduled visit (if applicable) ³	Early termination (if applicable) ¹	References (protocol section)
Visit type	Site	Site	Site	Site	Site	Site	Site	Tele- phone ⁴	Short Site	Tele- phone ⁴	Standard Site	Site	Site			
Visit window (days) ⁵	-3	NA	±3	±3	±3	±3	±3	±3	±3	±3	±3	±3	±3			
Patient-reported	d outcom	es (cont	inued)													
Worst Weekly Pruritus numeric rating scale Eczema-related																
Sleep numeric rating scale	X	X	X	X	X	X	X		X		X	X		X	X	11.3.2.4
Patient use of topical treatment ¹⁴																

- 1) If screening/baseline visits are performed on the same day as visit(s) in the parent trial, the order of assessments should be adhered to, working in parallel for both protocols. Assessments where data are captured in different vendor systems databases (ECG, ePRO, and laboratory tests) need to be completed twice. In such cases, the parent trial assessment should be performed first, followed by the trial LP0162-1337 assessment. For subjects included in the trial prior to protocol version 10, the first visit after May 2021 can be a site visit or a telephone visit.
- 2) Subjects who withdraw from the trial will be followed up as described in Section 10. The final safety follow-up visit will be 4 weeks after the last dose (i.e. 2 weeks after the EOT visit). For subjects from the parent trial LP0162-1334, the maximum number of weeks until the EOT visit will be 114 weeks.
- 3) Assessments and procedures to be performed at an unscheduled visit are at the discretion of the investigator. If the unscheduled visit involves administration of rescue treatment, the investigator should make every attempt to conduct efficacy and safety assessments (at least disease severity scores [IGA and EASI], concomitant medications/procedures, and AEs) immediately before administering any rescue treatment (see Section 9.5).

Trial ID: LP0162-1337

THIS DOCUMENT CONTAINS CONFIDENTIAL INFORMATION AND MUST NOT BE COPIED OR MADE AVAILABLE TO ANY THIRD PARTY WITHOUT THE PRIOR WRITTEN CONSENT OF THE LEO PHARMA GROUP

- 4) For subjects from the parent trial LP0162-1334, the telephone visit should preferably be performed as a video call.

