7.1.4 Safety follow-up period (after last IMP dose)

All subjects will complete an off-treatment follow-up period for the assessment of safety, PK, and ADA.

The timing of the safety follow-up visit depends on the parent trial and on whether the subject has consented to participate after May 2021, as summarised in Panel 8.

Panel 8: Safety follow-up visit

Parent trial	Subject did NOT consent to continue after May 2021	Subject DID re-consent or consent to participate after May 2021
LP0162-1325, -1326, -1334 (adolescents), -1339, -1341, -1342, -1343, -1346, and TRA-WEI-0015-I	16 weeks after last dose	4 weeks after last dose

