14.3.8.2 Vital signs

The change in vital signs (blood pressure, heart rate, body temperature) from baseline (in the current trial) to each visit will be summarised by visit as mean, SD, median, minimum, and maximum values. The changes will be presented for the total cohort of subjects and by tralokinumab-naïve/re-treated/continuously treated subjects.

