No testing has been specified.

3 Sample size

Sample size documentation is provided in the CTP Section 14.1.

4 Trial analysis sets

All screened subjects will be accounted for in the CTR.

All subjects receiving tralokinumab will be included in the FAS and will be analysed for efficacy. Exclusions from the FAS can be considered in special cases as described in ICH E9, section 5.2.1., Full Analysis Set. If it is decided to exclude a subject who has received tralokinumab from the FAS, a justification addressing ICH E9 will be given.

The SAF will be identical to the FAS, as all subjects receiving tralokinumab will be included in the SAF. However, subjects decided to be excluded from the FAS will not also be excluded in the SAF. Any exclusions from the SAF will be justified separately addressing ICH E9.

All subjects receiving tralokinumab and starting in the safety follow-up will be included in a safety follow-up analysis set. Any exclusions will be identical to the safety analysis set.

Data from the investigator-initiated parent trial TRA-WEI-0015-I will not be transferred to LEO Pharma. Thus, endpoints defined as change from baseline (in the parent trial) will not be calculated for subjects from this trial, and data from this trial will not be included in tables summarising endpoints defined as change from baseline or where data are presented by responder/non-responder status. Subjects from TRA-WEI-0015-I will be contributing to the primary endpoint and included in summary tables where possible.

The decisions regarding inclusion/exclusion of subjects or subject data from the trial analysis sets will be documented in the Classification Brief.

5 Statistical analysis

All presentations of data will be made for the total ECZTEND population with above analysis sets applied as appropriate.

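### The SAP's single safety follow-up (SFU) period combines windows of about 14 and about 2 weeks after end of treatment, so its AE percentages depend on the mix of schedules

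*SAP*

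**What the plan says.** Protocol Section 7.1.4 makes the follow-up length vary: "The timing of the safety follow-up visit depends on the parent trial and on whether the subject has consented to participate after May 2021". Panel 8 gives 16 weeks after last dose for subjects who did not consent to continue after May 2021 and 4 weeks for those who did, in all parent trials. The footnotes to Panels 4 and 5 restate these as 14 and 2 weeks after the EOT visit.

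Two further groups also had 16 weeks. The Section 4.1 schedule applied to subjects who withdrew before May 2021. The amendment history shows that continuing LP0162-1334 subjects kept 16 weeks under Amendment 7 until Amendment 9 (February 2022) shortened it.

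SAP Section 4 defines one analysis set: "All subjects receiving tralokinumab and starting in the safety follow-up will be included in a safety follow-up analysis set". SAP Section 5.8.1 presents the SFU period as a whole: "all AEs and SAEs will be presented by an overview summary and by SOC and PT using the safety follow-up analysis set". The summaries it lists for the treatment and SFU periods include percentages of subjects, numbers of events, and incidence and occurrence rates per 100 patient-years. Further AE summaries are planned for LP0162-1334, for prior-treatment groups, and before and after the end of May 2021. None is by follow-up length.

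**The concern.** The share of subjects with at least one event rises with the length of observation. If some subjects are observed seven times as long as others after EOT, a single percentage describes the mix of schedules as much as the off-treatment risk. An event type seen mainly late after the last dose would be diluted by subjects whose follow-up had already ended. Comparisons between LP0162-1334 and the total, or between naïve, re-treated and continuously treated subjects, could differ only because their mixes of follow-up length differ.

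The planned splits do not remove this. The calendar split, so far as it includes follow-up events, puts a subject who stopped at the end of May 2021 and then had 14 weeks of follow-up in the same table as later 2-week follow-ups. The LP0162-1334 group may itself contain both lengths.

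**Working it through.** **Inputs**
- Old schedule (Protocol 4.1, Panel 4 footnotes): "The final safety follow-up visit will be 16 weeks after the last dose (i.e. 14 weeks after the EOT visit").
- New schedule (Protocol 4.2, Panel 5 footnotes): "The final safety follow-up visit will be 4 weeks after the last dose (i.e. 2 weeks after the EOT visit").
- EOT timing (Protocol 4.1): "EOT = end of treatment, 2 weeks after the last dose of tralokinumab".
- Latest EOT on the old schedule: Week 140 (Panel 4).
- Exposure (SAP 5.4.3): first dose to the EOT visit or, if that is missing, to permanent discontinuation.
- AE rates and the proportion on each schedule: not in the documents, so assumed below.

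**Reproducing the plan's figures**
- Old schedule: 16 − 2 = 14 weeks after EOT. Latest SFU visit: 140 + 14 = Week 154, as stated in "SFU visit (maximum 154 weeks) for each subject will depend on the time of their trial entry and treatment duration".
- New schedule: 4 − 2 = 2 weeks after EOT.
- Ratio of windows: 14 / 2 = 7.

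**Effect on percentages**

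With a constant first-event rate λ per patient-year, the share with at least one event in w weeks is 1 − exp(−λ·w/52.18). The pooled figure is f × (14-week share) + (1 − f) × (2-week share), where f is the proportion with the long window.

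| Assumed λ | 14 weeks | 2 weeks | Pooled, f = 25% | f = 50% | f = 75% |
|---|---|---|---|---|---|
| 0.1 | 2.6% | 0.4% | 0.9% | 1.5% | 2.1% |
| 0.5 | 12.6% | 1.9% | 4.6% | 7.2% | 9.9% |
| 1.0 | 23.5% | 3.8% | 8.7% | 13.6% | 18.6% |
| 2.0 | 41.5% | 7.4% | 15.9% | 24.5% | 33.0% |

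At λ = 1.0: 1 − exp(−14/52.18) = 23.5% and 1 − exp(−2/52.18) = 3.8%. Within each row the underlying risk is the same throughout.

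The frequent-AE listing at 5% of subjects is also planned for the SFU period. A preferred term at an assumed 0.2 per patient-year gives 1 − exp(−0.2 × 14/52.18) = 5.2% in the long window, 0.8% in the short window and 3.0% pooled at f = 50%. Whether it is listed then depends on f.

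**Can the planned rates correct for length?**

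The mean window is 14f + 2(1 − f): 5, 8 or 11 weeks at f = 25%, 50% or 75%. Dividing events by this person-time would recover the same rate whatever the mix. The SAP's exposure stops at the EOT visit or at discontinuation, so this time is not in the defined denominator.

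**Drug level at the SFU visit (relevant only if by-visit tables include it)**

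Protocol 8.2 equates 16 weeks with 5 half-lives, so the half-life is 16/5 = 3.2 weeks. Assuming first-order decay and ignoring absorption, the residual is 2^(−4/3.2) = 42% at 4 weeks and 2^(−16/3.2) = 3% at 16 weeks.

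**The case against.** The strongest reply is that the SAP already lists rates per 100 patient-years for the SFU period, the usual remedy for unequal observation. That would answer most of the point if follow-up person-time were defined. It is not, so the reply shows what is missing rather than removing the problem.

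It can also be said that the SFU tables are descriptive, no testing is specified, no endpoint concerns off-drug effects and all AEs are listed. This stands and limits the severity, but it does not make a pooled percentage interpretable.

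Three stronger readings are tempting but unsupported:
- **Subgroup percentages will differ because of their mix.** They could, but no section reports the mix by subgroup, and the rates above are assumptions.
- **SFU laboratory, vital-sign, ECG and ADA results are pooled as one time point.** For vital signs the protocol says only that changes "from baseline (in the current trial) to each visit will be summarised by visit"; the laboratory text is similar. Inclusion of the SFU visit is an inference. The SAP names no SFU-specific ECG or ADA table.
- **Consent status alone fixes the length.** Earlier withdrawals and LP0162-1334 subjects who continued but stopped before Amendment 9 show otherwise.

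Two practical objections also stand. Withdrawn subjects have no EOT visit (Protocol 10.3), so a common window anchored at EOT would be undefined for them. The eCRF did not record non-consent to the extension as a withdrawal reason (SAP 5.2), so follow-up length must be derived.

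**Conclusion.** The point holds for the SFU AE and SAE percentages. The plan pools windows of about 14 and 2 weeks after EOT without a split by length or a person-time denominator that covers them. The seven-fold ratio follows from the documents. The size of the distortion does not: 23.5% against 3.8%, or a pooled figure anywhere from 8.7% to 18.6% as the long-window share goes from 25% to 75%, rests on an assumed constant rate of 1 first AE per patient-year and on assumed mixes. For withdrawn subjects and within the ±3-day visit windows, 14 and 2 weeks are approximate.

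For laboratory and vital-sign changes the point is conditional on the by-visit tables including the SFU visit. A reader might infer that the main safety result is compromised. It is not: the primary endpoint covers the treatment period, and the laboratory shift tables use end of treatment or the highest or lowest treatment-period value. The change is worth making because it is cheap and the trial's purpose is long-term safety. Nothing here bears on which follow-up length is appropriate.

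**What to change.** In SAP Sections 4 and 5.8.1:
1. Present the SFU AE/SAE overview and SOC/PT tables by each subject's applicable follow-up length, 16 or 4 weeks after last dose. Derive it from the protocol version followed and the last-dose and SFU visit dates, not from calendar date or parent trial alone.
2. Define SFU person-time as running from the EOT or early termination visit to the SFU visit or last contact, and use it for the SFU rates.
3. If a pooled SFU percentage is kept, limit it to SFU events starting within 4 weeks after last dose. Both schedules cover this period, apart from the visit window, and the anchor also works for subjects without an EOT visit.
4. If by-visit laboratory or vital-sign change tables include the SFU visit, show it separately for the two lengths.

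The cost is SAP wording, one derived grouping variable and a short derivation rule for withdrawals near May 2021; no new data are needed. The downside is smaller groups in each table.
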